In addition to the procedures in the Master Protocol that should be conducted during the phone or telemedicine and remote visits, the following regimen-specific procedures should be completed:

- Home Spirometry (Week 8 and 16 only)
- Voice Recording
- CNS Bulbar Function Scale (Week 8 and 16 only)
- *Neisseria Meningitidis* Vaccination booster shots

Details on collection of the CNS Bulbar Function Scale, dispensing IP during remote visits, and documenting participants' willingness to participate in OLE are described in the MOP.

Blood samples for anti-drug antibody sampling, PK and PD analyses, and peripheral blood biomarker samples are not collected during the remote visits by the home health agency and this should be recorded as such in the applicable source documentation and EDC.

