6.1.5 Week 8 Visit

Participants should be instructed to hold study drug on the day of the study visit. Study drug should not be taken until after study visit procedures are complete.

This visit will take place in-person 56 ± 7 days after the Baseline Visit. The following procedures will be performed:

- Home Spirometry
- CNS Bulbar Function Scale
- Voice Recording
- Anti-drug Antibody Sampling
- Zilucoplan Plasma PK Analysis
- Zilucoplan Pharmacodynamic Analysis
- Zilucoplan Peripheral Blood Biomarker Samples
- Dispense investigational product to participant
- Remind participant to bring investigational product to the next visit

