Abbreviations: ALD = after last dose, ALS = amyotrophic lateral sclerosis, ALSAQ-40 = ALS Assessment Questionnaire, ALSFRS-R = ALS Functional Rating Scale Revised, BP = blood pressure, C = completed only if the visit is conducted in-clinic, CBC = complete blood count, Cln = Clinic visit, CNS-BFS = Center for Neurologic Study Bulbar Function Scale, CSF = cerebrospinal fluid, C-SSRS = Columbia-Suicide Severity Rating Scale, d = day, DNA = deoxyribonucleic acid, ECG = electrocardiogram, LFTs = liver function tests, MP = Master Protocol, PD = pharmacodynamic, Phn = Phone visit, PK = pharmacokinetic, RGA = the zilucolan regimen, Scrn = Screening Visit.

¹ Master Protocol (MP) screening procedures must be completed between 42 days and 1 day prior to the Baseline Visit. If initial administration of conjugate and serotype B meningococcal vaccines is required, then MP screening procedures must be completed no fewer than 14 days prior to the Baseline Visit.

² RGA regimen-specific screening procedures must be completed no more than 41 days prior to the Baseline Visit. If initial administration of conjugate and serotype B meningococcal vaccines is required, then RGA regimen-specific screening procedures must be completed no fewer than 14 days prior to the Baseline Visit. Otherwise, RGA regimen-specific screening procedures may be completed on the same day as the Baseline Visit.

³ Participants should be instructed to hold the morning dose of study drug on the day of the Week 8, 16, and 24 study visits. Study drug should not be taken until after study visit procedures are complete.

⁴ Participants who are participating into the Open-label Extension (OLE) at the time scheduled for the Follow-up Safety Call will not complete a Follow-up Safety Call. Participants who continue into the OLE and then terminate prior to the time scheduled for the Follow-up Safety Call should be asked to complete a Follow-Up Safety Call.

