6.5.6 HHD0 and HHD0²

Analyses of HHD0 are the same as specified in the M-SAP with the addition of parallel analyses of HHD0², with a separate analysis that includes baseline serum NfL level as a covariate, and with the clarification that time to zero strength for both analyses is interval censored between HHD assessments.

Inference from these analyses is supportive of inference from the repeated-measures linear mixed model for HHD upper and lower extremity scores.

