Appendix 2. Immunogenicity Analyses

The incidence of anti-drug antibodies (ADA) and anti-PEG antibodies (anti-PEG-ADA) (immunogenicity against zilucoplan) will be measured via dual assay strategy consisting of measuring ADA and anti-PEG-ADA.

The ADA and anti-PEG-ADA status for both active and placebo participants will be determined for each pre-treatment (Baseline) and post-treatment visits (i.e., week 8, week 16 and week 24) where samples are taken for ADA analysis.

- Sample values that are either ‘negative screen’ or ‘positive screen’ and ‘negative immunodepletion’ will be defined as ADA negative
- Sample values that are ‘positive screen’ and ‘positive immunodepletion’ will be defined as ADA positive
- Samples that could not be tested for ADA status due to inadequate sample volume, mishandling, or errors in sample collection, processing, storage, etc, will be defined as Missing.

The following ADA classifications will be derived from the sample ADA status.

Table: ADA Classification

Classification	Classification Label	Definition
1	Pre-ADA negative – treatment induced ADA negative	Participants who are ADA negative at Baseline and ADA negative at all sampling points post-Baseline
2	Pre-ADA negative – treatment induced ADA positive	Participants who are ADA negative at Baseline and ADA positive at any sampling point post-Baseline. It also includes participants who have a missing pre-treatment sample (either missing or insufficient volume) at Baseline with one or more ADA positive post-Baseline samples.
3	Pre-ADA positive – treatment reduced ADA	Participants who are ADA positive at Baseline, and ADA negative at all sampling points post-Baseline
4	Pre-ADA positive – treatment unaffected ADA	Includes participants who are ADA positive at Baseline and ADA positive at any sampling point post-Baseline (including Observation Period) with titer values of the same magnitude as Baseline (less than a predefined fold difference from the Baseline value which will be defined within the validation of the assay, i.e., MSR of the assay).

Table: ADA Classification

Classification	Classification Label	Definition

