- The first occurrence of treatment-emergent ADA positive (Classification 2 and 5) will be summarized using frequency and percentage at each post-Baseline visit by treatment group. Study participants will be counted only once in the numerator based on the earliest visit at which treatment-emergent ADA positivity is observed. At other visits, study participants will be counted in the denominator (assuming a measurement is available). Missing measurements will not be included in the denominator.
- The time to achieving treatment-emergent ADA positivity, separated by treatment group, will be summarized and analyzed based on Kaplan-Meier methods. Study participants will be considered to have an event at the time point at which treatment-emergent ADA positive is first achieved. Participants who never had a treatment-emergent ADA positivity will be censored at the date of their last visit. This will also be plotted graphically.

The same tables will be provided for anti-PEG-ADA by treatment group.

Relationship between ADA and Safety Endpoints

TEAEs will be summarized by ADA status using the following categories:

- AEs starting before first treatment emergent ADA positive result
- AEs starting on or after first treatment emergent ADA positive result
- AEs for study participants who were overall ADA negative

Each TEAE will be classified according to whether it occurred before the first treatment emergent positive result, on or after the first treatment positive result, or for a study participant that remained treatment negative post-baseline. If a participant has multiple reports of the same AE (i.e., those which code to the same preferred term) emerging both prior to first ADA positive result and after first ADA positive result, both events will be counted in the appropriate category.

The following AE outputs will be presented this way:

- Overall summary of TEAEs (i.e., the number of events and proportion of participants experiencing any TEAE, any serious TEAE, any severe TEAE, any related TEAE, any TEAE leading to discontinuation of study drug, and any fatal TEAEs) by treatment group and by ADA status
- Incidence of TEAEs of interest by treatment group and by ADA status
Presented for any hypersensitivity reactions and any injection site reactions (as defined in Appendix 1) and any autoimmune disorders (defined by the MedDRA HLGT of Autoimmune disorders).

The AE analyses above will be repeated by anti-PEG-ADA status.

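### Splitting adverse events at the first ADA-positive sample, with planned samples at least 8 weeks apart, books some post-seroconversion events as 'before' and weakens the within-converter before versus on/after contrast

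*SAP*

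**What the plan says.** SAP Appendix 2, under the relationship between ADA and safety endpoints, sets the rule: "Each TEAE will be classified according to whether it occurred before the first treatment emergent positive result". The other two categories are "AEs starting on or after first treatment emergent ADA positive result" and "AEs for study participants who were overall ADA negative". The tables give numbers of events and proportions of participants. They are repeated for anti-PEG-ADA.

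ADA status is determined at Baseline and at "post-treatment visits (i.e., week 8, week 16 and week 24) where samples are taken for ADA analysis". In the SAP section 2.9 schedule, Weeks 8 and 16 carry the code defined as "C = completed only if the visit is conducted in-clinic". Protocol section 6.1 agrees: "Blood samples for anti-drug antibody sampling, PK and PD analyses, and peripheral blood biomarker samples are not collected during the remote visits". Appendix 2 counts unscheduled samples in its cumulative and overall ADA status, but no section requires any.

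Appendix 2 gives no look-back, midpoint rule or separate category for the time between the last sample short of treatment-emergent positivity and the first that reaches it. SAP section 6.6.6 assigns these analyses to the sponsor, in a separate immunogenicity report.

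**The concern.** The date of a first positive sample is a detection date. Seroconversion happened at some unknown time after the previous sample. A participant who converts on Day 60 and is next sampled on Day 112 has up to 52 days of antibody exposure whose events are tabulated as 'before'.

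Elsewhere the SAP allows for this kind of observation. For HHD0 and HHD0², section 6.5.6 says "time to zero strength for both analyses is interval censored between HHD assessments", and sections 5.11 and 6.5.4 treat King's stage 4a or 4b the same way.

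The outputs cover hypersensitivity, injection-site reactions and autoimmune disorders. If antibodies provoke such events at or soon after they appear, some of those events move into the comparison window, and the error runs towards reassurance.

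**Working it through.** The documents give no figure for this split, so there is none to reproduce.

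**Inputs from the documents**
- Planned samples: Days 0, 56, 112 and 168, so each gap is 56 days. Protocol section 6.1.5 reads "This visit will take place in-person 56 ± 7 days after the Baseline Visit", and Weeks 16 and 24 have the same tolerance, so two post-baseline samples can be 56 + 14 = 70 days apart.
- Remote visits: a gap of 112 days if Week 8 or Week 16 is remote, and 168 days if both are.
- End of the TEAE interval (SAP section 6.6.1): the first OLE dose, taken as Day 168; or 40 days after the last dose, taken as Day 208, without the OLE.

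**Assumptions, not in the documents:** conversion uniform over Days 0 to 168 (mean Day 84); a constant event rate that is multiplied by R from the day of conversion; no dropout; a perfect assay; no unscheduled samples.

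**Lag with all samples taken.** Mean day of first positive = (56 + 112 + 168)/3 = 112. Mean lag L = 112 − 84 = 28 days.

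**Share of antibody-positive time booked as 'before'.** To Day 168: 28/(168 − 84) = 33%. To Day 208: 28/(208 − 84) = 23%.

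**Apparent rate ratio, on/after to before.** The 'before' window averages 84 + L days and contains 84 + L×R events in units of the background rate, so

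apparent ratio = R × (84 + L) / (84 + L×R).

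| Week 8 and 16 samples | Mean first positive (day) | L (days) | True R = 2 appears as |
|---|---|---|---|
| Both taken | 112 | 28 | 224/140 = 1.60 |
| One missed | (112 + 112 + 168)/3 = 130.7 | 46.7 | 261.3/177.3 = 1.47 |
| Both missed (needs follow-up past Day 168) | 168 | 84 | 336/252 = 1.33 |

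With both taken, R = 1.5 appears as 168/126 = 1.33 and R = 3 as 336/168 = 2.00. The end of follow-up does not enter the formula.

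**On the planned scale (counts).** To Day 168, the mean on/after time is 168 − 112 = 56 days.
- R = 2: before 84 + 28×2 = 140, on/after 2×56 = 112. Splitting at seroconversion would give 84 and 2×84 = 168, so the order reverses.
- R = 1: 112 against 56, a 2:1 difference with no antibody effect. This comes purely from unequal time at risk.

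**On/after versus ADA-negative.** No gap time enters the on/after group, so under these assumptions the rate ratio is R. As counts per participant at R = 2, it is 2×56 = 112 against 168 for an ADA-negative participant followed to Day 168. A doubled rate then looks like fewer events.

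**Check on the three-window split.** Window 1, up to the last negative sample, averages (0 + 56 + 112)/3 = 56 days, all before conversion. Window 3 is all after conversion, so the ratio of rates is R. Counts would still mislead: to Day 208, window 3 averages (152 + 96 + 40)/3 = 96 days, and 96/56 = 1.7 with no effect. Keeping two windows but cutting at the last negative sample does not recover R. At R = 2 it gives (28 + 2×84)/112 = 1.75 to Day 168, or (28 + 2×124)/152 = 1.82 to Day 208.

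**The case against.** - **The label is accurate.** The category refers to the first positive result and claims no conversion date. Gap events that truly precede seroconversion are placed correctly. This stands: the weakness lies in reading the table as before and after antibodies.
- **The SAP plans no rate ratio here.** It plans counts and proportions, with no test of this contrast. This stands. The 1.60 measures the misclassification and is not a forecast of a reported result.
- **A reader might infer that the split dilutes any antibody-related harm.** The documents do not support that. The third category gives an on/after versus ADA-negative comparison free of this misclassification, and harm that begins well after antibodies appear is little affected. That comparison still needs time at risk.
- **HHD0 and King's stage are time-to-event endpoints, whereas this is a cross-tabulation.** The closer counterpart is Appendix 2's Kaplan-Meier analysis of time to ADA positivity, which also uses the detection time. The analogy is therefore imperfect, but it shows that the SAP recognises events seen only at visits.
- **Some participants have no earlier negative sample.** Treatment-emergent positivity includes Classification 5 (positive at Baseline, then boosted) and those in Classification 2 with a missing Baseline sample. This stands, and any fix needs a rule for them.

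**Conclusion.** The point holds for one contrast: before versus on/after among treatment-emergent positive participants, when harm starts at or soon after seroconversion. Under that condition the direction is towards no effect. The size rests on the assumed uniform conversion and constant rates: a mean lag of 28 days, with a true ratio of 2 appearing as 1.60 with full sampling, 1.47 with one of Weeks 8 and 16 missed, and 1.33 with both missed. Unscheduled samples would shorten the lag. The documents do not say how many visits were remote.

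The absence of time at risk is a companion problem at least as large, since counts differ 2:1 with no effect (follow-up to Day 168). It also affects the ADA-negative comparison.

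A reader might infer that the trial's safety conclusions are compromised. They are not: this is a descriptive analysis in a separate report, and neither the efficacy analyses nor the main TEAE summaries depend on it. It is worth correcting because the correction is cheap.

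**What to change.** In Appendix 2, for both ADA and anti-PEG-ADA, divide the TEAEs of treatment-emergent positive participants into three windows:

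1. up to and including the last sample that does not meet the treatment-emergent definition;
2. after that sample and before the first treatment-emergent positive sample, labelled *status unknown*;
3. on or after the first treatment-emergent positive sample.

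If no such earlier sample exists (for example, Baseline missing and the first post-Baseline sample positive), time from first dose to the first positive is *status unknown*. For boosted (Classification 5) participants, window 1 ends at the last sample below the boost threshold.

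Report participant-time and events per 100 participant-years for each window and for the ADA-negative group, the unit SAP section 6.6.1 already uses for TEAEs. Compare window 1 with window 3.

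The cost is SAP wording and one more column from dates already held. The downside is smaller cells. A Baseline-negative participant first positive at Week 8 contributes essentially no on-treatment time to window 1, and one first positive at Week 24 who enters the OLE contributes essentially none to window 3, so the comparison is partly between different participants.

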6.1.7 Week 16 Visit

Participants should be instructed to hold study drug on the day of the study visit. Study drug should not be taken until after study visit procedures are complete.

This visit will take place in-person 112 ± 7 days after the Baseline Visit. The following procedures will be performed:

- Home Spirometry
- CNS Bulbar Function Scale

- Voice Recording
- Anti-drug Antibody Sampling
- Zilucoplan Plasma PK Analysis
- Zilucoplan Pharmacodynamic Analysis
- Zilucoplan Peripheral Blood Biomarker Samples
- Document participant's willingness to participate in the OLE
 - If OLE consent is not obtained at Week 16, it may be obtained at Week 24.
- Dispense investigational product to participant
- Remind participant to bring investigational product to the next visit

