6.6 Safety Analyses

6.6.1 Treatment-emergent Adverse Events

Summaries and analyses of treatment-emergent adverse events (TEAE) are the same as specified in the M-SAP with the following revisions.

TEAEs are defined as those adverse events with onset dates in the interval from double-blind treatment initiation to the earliest of the Final Safety Visit, the date the participant dies, early terminates, or is lost to follow-up, 40 days after last dose of study drug, or the date of first dose of study drug during participation in the OLE, if so exposed. Adverse events with onset on the day of double-blind treatment initiation and adverse events with incompletely specified onset date where the ambiguous date spans the day of double-blind treatment initiation or the earliest of the events above that define the end of the treatment-emergence interval will be assumed to be treatment emergent except for those known to precede first exposure to study drug.

In addition to summaries specified in the M-SAP, all adverse events, including those not classified as TEAEs, will be summarized by Medical Dictionary for Regulatory Activities (MedDRA) system organ class and preferred term and serious TEAEs will be summarized by MedDRA system organ class, high level term, and preferred term for all TEAEs. In addition, TEAEs will be summarized by MedDRA system organ class and preferred term for fatal TEAEs, TEAEs that occurred during a participant's COVID-19 infection (defined as 5 days prior to symptom onset to end of COVID-19 symptoms or the earlier of 91 days after symptom onset or the end of double-blind follow-up, if ongoing), TEAEs of interest, TEAEs of interest stratified by severity, serious TEAEs of interest, and TEAEs and serious TEAEs stratified by the following subgroups: baseline riluzole use, baseline edaravone use, age, sex, race, ethnicity, weight, BMI, and CKD stage. Subgroup classifications will be the same as described in Section 6.5.10 Subgroup Analyses except that the "other" group will be retained regardless of prevalence.

TEAEs indicating COVID-19 infection are the following: Asymptomatic COVID-19, COVID-19, COVID-19 pneumonia, COVID-19 treatment, Post-acute COVID-19 syndrome, SARS-CoV-2 antibody test positive, SARS-CoV-2 RNA increased, SARS-CoV-2 sepsis, SARS-CoV-2 test false negative, SARS-CoV-2 test positive, SARS-CoV-2 viraemia, Suspected COVID-19. TEAEs of interest are defined in Appendix 1 of this R-SAP.

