Treatment-dependent differences in the proportion of participants experiencing a given type of TEAE will not be tested. Treatment-dependent differences in TEAE incidence rates in units of number per 100 participant years will be estimated as differences rather than ratios and will include comparison-wise 95% confidence intervals with variance estimates obtained by the delta method.

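### The overall TEAE summary by ADA status uses counts and proportions over windows of unequal length, so the post-positive category is biased low against ADA-negative participants and can mask an ADA-related excess

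*SAP*

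**What the plan says.** SAP Appendix 2, under the relationship between ADA and safety endpoints, sorts each TEAE by the ADA status of the participant at onset. A participant who seroconverts has events divided at the first positive sample; one of the resulting categories is "AEs starting on or after first treatment emergent ADA positive result". A participant who is overall ADA negative contributes the whole interval to a third category.

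Two outputs follow, each by treatment group and ADA status and each repeated for anti-PEG-ADA:

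- An overall TEAE summary, defined as "the number of events and proportion of participants experiencing any TEAE", with the same for serious, severe, related, discontinuation-leading and fatal TEAEs.
- The incidence of selected TEAEs of interest: hypersensitivity, injection site reactions and autoimmune disorders. Appendix 2 does not say whether incidence here is a proportion or a rate.

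Scheduled ADA status comes from baseline and from "post-treatment visits (i.e., week 8, week 16 and week 24) where samples are taken for ADA analysis". SAP Section 6.6.1 closes the TEAE interval at the earliest of several dates, including 40 days after the last dose "or the date of first dose of study drug during participation in the OLE, if so exposed". The same section plans treatment differences in "TEAE incidence rates in units of number per 100 participant years", but Appendix 2 does not carry that measure over to ADA status. It gives no person-time, denominator rule or time-dependent method for these tables.

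**The concern.** A count, or the proportion with at least one event, grows with the time over which events can be seen. The three ADA categories have different observation times by construction: a seroconverter's follow-up is cut in two, while an ADA-negative participant's is left whole. Equal underlying event rates will therefore give unequal table entries.

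The tables are where a reader would look for adverse events that follow antibody formation. If the after category has little time in which to record events, a low figure there reads as reassurance when it may only reflect lack of observation. The extreme case is a first positive at Week 24 in a participant who then starts open-label drug: the TEAE interval closes almost at once, and the entry is close to 0% whatever the antibodies do.

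**Working it through.** The documents give no event rate or expected result for this output, so there is no planned figure to reproduce. The check derives the window lengths from the documents and applies one constant event rate to all of them.

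**Inputs from the documents**

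- Week 8: "This visit will take place in-person 56 ± 7 days after the Baseline Visit" (Protocol 6.1.5).
- Week 16: "This visit will take place in-person 112 ± 7 days after the Baseline Visit" (Protocol 6.1.7).
- Week 24: day 168 ± 7 (Protocol 6.1.9).
- End of the TEAE interval (SAP 6.6.1), for a participant dosed to Week 24: about day 168 with OLE entry at that visit, or 168 + 40 = day 208 without.

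**Assumptions**

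- Nominal visit days and completion of 24 weeks.
- First positive at a scheduled sample.
- Proportions taken over the participants in each category.
- A constant event rate r per participant-year, equal in all windows, so there is no ADA effect. r is not in the documents; the range tried is 0.5 to 8.

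**Step 1: window lengths.** Before = day of first positive. After = end day − day of first positive. ADA negative = end day.

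| First positive | Before (days) | After, OLE | After, no OLE | After ÷ ADA negative, OLE | After ÷ ADA negative, no OLE |
|---|---|---|---|---|---|
| Week 8 | 56 | 112 | 152 | 112/168 = 0.67 | 152/208 = 0.73 |
| Week 16 | 112 | 56 | 96 | 56/168 = 0.33 | 96/208 = 0.46 |
| Week 24 | 168 | about 0 | 40 | about 0 | 40/208 = 0.19 |
| Never (ADA negative) | – | 168 (whole) | 208 (whole) | – | – |

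On nominal days even the longest after window (152) is shorter than the shortest ADA-negative window (168).

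**Step 2: expected table entries at r = 2.** Events per 100 participants = 100·r·t/365.25. Proportion with at least one event = 1 − exp(−r·t/365.25). Example: t = 112 gives 61.3 events per 100 and 45.8%; t = 168 gives 92.0 and 60.1%.

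| First positive | OLE: before / after / ADA negative | No OLE: before / after / ADA negative |
|---|---|---|
| Week 8 | 26.4% / 45.8% / 60.1% | 26.4% / 56.5% / 68.0% |
| Week 16 | 45.8% / 26.4% / 60.1% | 45.8% / 40.9% / 68.0% |
| Week 24 | 60.1% / about 0% / 60.1% | 60.1% / 19.7% / 68.0% |

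The ordering is the same at every rate tried. For Week 8 with OLE, before / after / ADA negative is 7.4% / 14.2% / 20.5% at r = 0.5 and 70.7% / 91.4% / 97.5% at r = 8.

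**Step 3: pooling.** The planned table pools all seroconversion times. Illustrative mixes at r = 2:

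| Mix at Weeks 8/16/24 | OLE: before / after / ADA negative | No OLE: before / after / ADA negative |
|---|---|---|
| 100/0/0% | 26.4% / 45.8% / 60.1% | 26.4% / 56.5% / 68.0% |
| 60/30/10% | 35.6% / 35.4% / 60.1% | 35.6% / 48.1% / 68.0% |
| Equal thirds | 44.1% / 24.1% / 60.1% | 44.1% / 39.0% / 68.0% |
| 10/30/60% | 52.5% / 12.5% / 60.1% | 52.5% / 29.7% / 68.0% |

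Before versus after changes sign across mixes and nearly vanishes in one. After versus ADA negative is low in all of them.

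**Step 4: size of excess that could be hidden.** Counts and proportions in the after and ADA-negative categories are equal when (rate after) × (time after) = (rate negative) × (time negative), so the true rate ratio that would look like no difference is the ratio of the windows. Week 8: 168/112 = 1.5 with OLE, 208/152 = 1.4 without. Week 16: 168/56 = 3.0 and 208/96 = 2.2. Week 24 without OLE: 208/40 = 5.2. These ratios do not depend on r.

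**Step 5: with person-time.** Week 8, OLE: 61.3 events over 100 × 112/365.25 = 30.7 participant-years is 200 per 100 participant-years; ADA negative, 92.0 over 100 × 168/365.25 = 46.0 is also 200. The ratio is 1.0 for every window of non-zero length.

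**The case against.** The strongest reply has five parts.

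- **Which output.** Counts and proportions are explicit only for the overall TEAE summary. A reader might infer that hypersensitivity, injection site and autoimmune events are reported the same way. Appendix 2 says only incidence, while Section 6.6.1 uses incidence rates per participant-year. This stands: for those events the documents show an undefined metric, and the bias follows only if a proportion is meant.
- **Direction.** A reader might also infer that the before/after contrast is bound to mislead, or that the table mainly measures window length. The documents do not support this. They give no seroconversion timing, and the pooled contrast can nearly cancel (35.6% versus 35.4% in one mix). What remains is the comparison with ADA-negative participants, which is low in every case worked here.
- **Purpose.** The summaries are descriptive and exploratory, carry no test, and under Section 6.6.6 go to a separate immunogenicity report. A reading that they decide whether antibodies cause events, or bear on efficacy, goes too far.
- **Context already planned.** Appendix 2 also tabulates first treatment-emergent positivity by visit and a Kaplan-Meier time to positivity. These let a careful reader gauge the window lengths roughly, but they do not correct the entries.
- **Unseen source.** Section 6.6.1 otherwise defers to the M-SAP, which was not available. A denominator convention there cannot be excluded, though Appendix 2 does not refer to it for these tables.

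It is also fair that rates are not a complete cure. If the hazard changes with time on drug, before and after rates differ without any ADA effect. The first positive sample can lag seroconversion by up to about 8 weeks on the scheduled sampling. Fatal events before a first positive sample are largely excluded from the before category by construction.

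**Conclusion.** The point holds for the overall TEAE summary as written. For participants completing 24 weeks, the after window is about 0 to 0.73 of the ADA-negative window with the same OLE choice. With no ADA effect the after category therefore shows fewer events per participant and a smaller proportion affected, and a true rate ratio of about 1.4 to 5.2, depending on the week of first positivity and OLE entry, could appear as no difference. A Week 24 first positive with immediate OLE entry carries almost no information.

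The window lengths rest on nominal visit days and full follow-up; the percentages also rest on an assumed constant rate, while the ordering does not depend on its value between 0.5 and 8 per participant-year. Early termination, unscheduled samples and visit windows would shift the lengths but would not make them equal in general.

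The before/after distortion has no fixed direction, and the extension to TEAEs of interest is conditional on what incidence means. The consequence is for interpretation of immunogenicity safety, not for primary inference.

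**What to change.** In Appendix 2, for both the overall TEAE summary and the TEAEs of interest, and for the anti-PEG-ADA repeats:

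- Add person-time and TEAE rates per 100 participant-years in each ADA category. Split each seroconverter's person-time at the date of the first treatment-emergent positive sample and end all person-time at the Section 6.6.1 TEAE cut-off.
- State whether incidence is a proportion or a rate, and give the denominator for any proportion.
- Print person-time beside every proportion, and mark windows of zero length as not estimable rather than 0%.
- Note under the tables that rates remove the window-length artefact but not changes in hazard over time or the lag between seroconversion and sampling.

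The cost is SAP wording and slightly more programming for the person-time split. No new data and no change to trial conduct are needed, and the rate measure is already planned in Section 6.6.1 for treatment differences.
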